5.5.2. Measurement of Compliance

Study treatment compliance parameters will be descriptively summarized using the number of patients with data, mean, SD, median, minimum and maximum for the variables listed in Section 4.5. According to protocol, cases of overdose are reported in the AE e-CRF pages and will be described in the AE analysis.

Both monitored and derived protocol deviations will be summarized for important deviations (counts of deviations), patients (incurring a deviation by count and percentage), and by type of important deviation (patient count and percentage). A patient listing of all important and minor protocol deviations will be provided.

5.6. Analyses of Efficacy Variables

For statistics where international and conventional units do not impact the results (e.g. percent changes from baseline, rates of patients below a threshold), derivations will be calculated and summaries will be run using conventional units. For other statistics (e.g. values at baseline and over time, absolute changes from baseline), derivations will be presented in both international and conventional units.

5.6.1. Analyses of Efficacy Variables

All lipid and special lipid measurements obtained from the central laboratory will be used to provide a value for the efficacy variables, if appropriate. The baseline value will be defined as the last available value before the first dose of double-blind study treatment in the neurocognitive function study (R727-CL-1532).

The efficacy variables will be explored through descriptive statistics at each scheduled visit, including the assessment prior to the first dose of the open-label study administration. The descriptive summaries will be performed in the Safety Analysis Set (for on-treatment analysis). Formal statistical testing is not planned.

Continuous variables will be summarized using the number of patients with data, mean, SD, median, first quartile (Q1) and third quartile (Q3), minimum and maximum.

Categorical variables (including the binary outcome variables) will be described by patient frequency of occurrence.

Descriptive statistics for calculated LDL-C will also be provided for patients with or without any study medication modification, separately.

Protocol schedule visits will be assigned to the Analysis Windows (See Appendix 10.1).

5.6.2. Sub-group Analyses

The subgroup analyses will be performed for LDL-C.

The following subgroups of interest will be evaluated, assuming there are enough patients in each subgroup level to perform the evaluation.

- The age group ($<65, \ge 65$),
- Gender (Female, Male),
- BMI ($<30 \text{ kg/m}^2$, $\geq 30 \text{ kg/m}^2$),
- Statins with versus without other LMT at baseline,

5.6.3. Adjustment for Multiple Comparisons

Adjustments to the alpha level for the purposes of multiple testing are not applicable for this safety study.

5.7. Analysis of Safety Data

The summary of safety results will be presented on the safety population (Section 3.1). No formal inferential testing will be performed. Summaries will be descriptive in nature. All summaries of safety results described below will be presented for each period respectively, unless otherwise noted.

General common rules

All safety analyses will be performed, unless otherwise specified, using the following common rules:

- Safety data in patients who do not belong to the safety population (i.e., exposed but not enrolled) will be listed separately.
- The baseline value will be defined as the last available value before the first dose of double-blind study treatment in the neurocognitive function study (R727-CL-1532).
- PCSA values are defined as abnormal values considered medically important by the Sponsor according to predefined criteria/thresholds based on literature review and defined by the Sponsor for clinical laboratory tests and vital signs (PCSA version dated January 2009 [Appendix 10.3]). Considering that the threshold defined in the PCSA list for monocytes and basophils can be below the ULN, the following PCSA criterion will be used for the PCSA analysis of monocytes and basophils:
 - PCSA criterion for monocytes: >0.7 Giga/L or >ULN (if ULN ≥ 0.7 Giga/L).
 - PCSA criterion for basophils: >0.1 Giga/L or >ULN (if ULN ≥ 0.1 Giga/L).

- PCSA criteria will determine which patients had at least 1 PCSA during the TEAE period, taking into account all evaluations including nonscheduled or repeated evaluations.
- The treatment-emergent PCSA denominator for a given parameter will be based on the number of patients assessed for that given parameter at least once during the TEAE period.
- All measurements, scheduled or unscheduled, fasting or not fasting, will be assigned to analysis windows defined in Appendix 10.1, Table 1 in order to provide an assessment for week 8 to week 96 time points.
- For quantitative safety parameters including central laboratory measurements and vital sign scores, descriptive statistics will be used to summarize results and change from baseline values by visit, the last on-treatment value and the worst on-treatment value. The last on-treatment value is defined as the last post-baseline value collected during the respective treatment period (as defined in Section 4.7.1). The worst on-treatment value is defined post-baseline as the nadir and/or the peak value collected during the respective treatment period, according to the direction (minimum or maximum) of the abnormality as defined in the PCSA list.
- Analyses performed according to diabetes status will be done considering diabetic patients as patients with either type 1 or type 2 diabetes in the medical history e-CRF page (regardless of the ongoing status) in the neurocognitive function study (R727-CL-1532).

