4.7. Safety Variables

Patient safety will be assessed through the collection of reported adverse events (AEs), clinical laboratory data, and vital signs. Unless otherwise noted, the baseline value is defined as the last available value before the first dose study treatment.

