4.7.1. Adverse Events Variables

The period of safety observation starts from the time when the patient gives informed consent and continues into the following periods:

- The PRE-TREATMENT period: defined as the time from the signed informed consent up to the first study treatment injection.
- The treatment-emergent adverse event (TEAE) period: defined as the time from the first dose of study drug to the last study visit.
- The POST-TREATMENT period: defined as starting the day after the end of the TEAE periods up to the patient's end of study.

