4.7.1.2. Adverse Events of Special Interest

Adverse events of special interest (AESI) are AEs (serious or non-serious) required to be monitored, documented, and managed in a pre-specified manner as described in the protocol.

In this study, AESI are the following (their complete descriptions are provided in the protocol):

- Local injection site reactions, selected using an e-CRF specific tick box on the AE page;
- General allergic events will be tabulated. Events will be selected using standardized MedDRA query (SMQ) "hypersensitivity" (broad and narrow) excluding the preferred terms linked to local injection site reactions (i.e. preferred terms containing "injection site" or "infusion site")
- ALT ≥3 ULN in the case baseline ALT < ULN or ALT ≥2 times the baseline value in the case baseline ALT ≥ ULN, selected using laboratory data. Baseline to be considered is the baseline of the present OLE study.
- Neurologic events selected using SMQs "demyelination" (broad and narrow), "peripheral neuropathy" (broad and narrow), and "Guillain-Barre syndrome" (broad and narrow) excluding the following preferred terms: "acute respiratory distress syndrome", "asthenia", "respiratory arrest" and "respiratory failure" and including selected PTs from SMQ "optic nerve disorders" (see Appendix 10.3, Table 3 for the list of terms)

- Symptomatic overdose with investigational medicine product, selected using HLT "Overdose" and the tick box "Symptomatic Overdose" in the e-CRF AE page.
- Pregnancy of female patient/subject (including male subject's partner), selected using appropriate MedDRA codes (PT "Pregnancy").
- Neurocognitive events:
 - Selected using a company MedDRA query (CMQ), based on the following 5 HLGTs: "deliria (including confusion)", "cognitive and attention disorders and disturbances", "dementia and amnestic conditions", "disturbances in thinking and perception", and "mental impairment disorders".
 - A second grouping of terms for neurocognitive events was defined based on Regulatory Agency request (FDA CMQ) (see Appendix 10.3, Table 4 for the list of terms)
- Cataract using HLT "Cataract conditions"
- New onset of diabetes (NOD) will be assessed in patients without diabetes at baseline (defined as patients without diabetes at baseline and during the study in the neurocognitive function study (R727-CL-1532)): The definition of new onset of diabetes (NOD) will be the following:

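### Outside ALT and new-onset diabetes, safety change is measured from the parent-study baseline, so ex-placebo on-treatment and treatment-emergent tables can include change that arose on placebo

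*SAP*

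**What the plan says.** **Governing rule.** The common rules in SAP 5.7 state: "The baseline value will be defined as the last available value before the first dose of double-blind study treatment", meaning the parent study R727-CL-1532. SAP 6.1 and protocol 10.4.2 and 10.5 agree.

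**Counting period.** The TEAE period in SAP 4.7.1 is "defined as the time from the first dose of study drug to the last study visit". PCSAs are counted within it, and SAP 5.7 labels them accordingly: "The treatment-emergent PCSA denominator for a given parameter will be based on the number of patients assessed for that given parameter". For quantitative parameters, descriptive statistics will "summarize results and change from baseline values by visit, the last on-treatment value and the worst on-treatment value".

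**Reporting groups.** SAP 5 reports ex-placebo, ex-PRALUENT and Overall.

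**Criteria that contain a change from baseline** (SAP 5.7.2 and Appendix 10.2):
- creatinine, 30% and 100% change;
- hemoglobin decrease of 15 g/L and of 20 g/L;
- weight, 5% up or down;
- heart rate, SBP and DBP, each combined with an absolute limit.

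The main laboratory PCSA table is also split by PCSA status at baseline, with normal and missing combined (SAP 5.7.2 and 6.3).

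**Two exceptions** (SAP 4.7.1.2). For the ALT increase, "Baseline to be considered is the baseline of the present OLE study". New-onset diabetes is assessed only in patients without diabetes, "defined as patients without diabetes at baseline and during the study in the neurocognitive function study (R727-CL-1532").

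**Competing wording.** SAP 4.7 says that for safety variables "the baseline value is defined as the last available value before the first dose study treatment", without naming the study. SAP 4.7.1 then uses study treatment for the OLE drug: the pre-treatment period is "defined as the time from the signed informed consent up to the first study treatment injection". SAP Appendix 10.1 defines Day 1 once by the first double-blind dose and once by the first IMP injection.

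**The concern.** Ex-placebo patients are the only ones who start PRALUENT in this study, so their column is where a reader looks for change after starting the drug. Under SAP 5.7 that column starts its clock at parent randomization while counting flags only from the first OLE dose.

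A shift that occurred wholly on placebo and persisted is then presented as on-treatment change or as a treatment-emergent PCSA. The reverse can also happen: a placebo-period shift in the opposite direction can hide a real change on PRALUENT. A laboratory abnormality that began on placebo and persists appears in the row for patients normal or missing at baseline, which reads as new onset.

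The SAP avoids this for ALT and for new-onset diabetes, but gives no reason for leaving the other parameters on the older baseline. Because SAP 4.7 can be read as the OLE baseline, two programmers could also build different safety tables from the same plan.

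**Working it through.** **1. Offset.** The parent treatment period is 96 weeks (protocol 3.2.1; SAP 1.1). The parent end-of-study visit is OLE visit 1 (protocol 5.1), so there is no further gap. Parent baseline therefore lies about 96 weeks before the first OLE dose.

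**2. What the change tables contain.** For an ex-placebo patient at OLE week w:

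change = (EOS value − parent baseline) + (week-w value − EOS value)

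The first term arises on placebo and the second on PRALUENT. The planned change tables show only the sum. Actual values are also tabulated by visit, but the windows in Appendix 10.1 start at week 8. The efficacy section (SAP 5.6.1) includes the assessment before the first OLE dose; the safety section specifies no such summary.

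**3. Effect on a flag.** Take the hemoglobin criterion (decrease of at least 15 g/L):
- Falls 15 g/L on placebo, then stable: −15 + 0 = −15 from the parent baseline (flagged); 0 from the OLE baseline (not flagged).
- Rises 15 g/L on placebo, then falls 15 g/L on PRALUENT: +15 − 15 = 0 from the parent baseline (not flagged); −15 from the OLE baseline (flagged).

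PCSAs defined only by a threshold keep the same total count under either baseline; only their split by baseline status moves.

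**4. Share of the interval before the first OLE dose**, 96/(96 + w):

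| OLE week | Calculation | Share |
|---|---|---|
| 24 (first post-dose safety laboratory visit) | 96/120 | 80% |
| 48 (first post-dose vital-sign and weight visit) | 96/144 | 67% |
| 96 | 96/192 | 50% |
| 192 | 96/288 | 33% |

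These are shares of calendar time. They would be shares of change only if change accrued evenly over time.

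**5. Possible size, illustration only.** The documents give no variability or drift, so these inputs are assumed. Simulated weight decrease of at least 5% at week 48 or 96, with no drug effect:

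| Assumption | Parent baseline | OLE baseline |
|---|---|---|
| Stable patient means, visit SD 2% | 6.9% | 6.9% |
| Stable patient means, visit SD 3% | 19.7% | 19.7% |
| Random-walk drift SD 3% per 96 weeks, measurement SD 1% | 16.5% | 7.9% |
| Random-walk drift SD 6% per 96 weeks, measurement SD 1% | 33.8% | 25.5% |

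The excess runs from zero, when nothing lasting happens on placebo, to about 8 to 9 percentage points under these drifts. By week 192 it narrows: 25.9% against 19.0% at SD 3%, and 44.4% against 40.6% at SD 6%.

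**6. Day 1 wording.** If Day 1 were the first double-blind dose, an OLE week-24 value would fall on study day 672 + 169 = 841, which is the week-120 target in Appendix 10.1. The windows therefore work only from the first OLE dose, and the other Day 1 sentence conflicts with them.

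**The case against.** The parent baseline is pre-specified and stated repeatedly. It suits the aim of describing exposure of about 6 years, and for ex-PRALUENT patients it validly gives cumulative change on drug. The study was stopped early on January 31, 2020, all analyses are descriptive, and no test or decision depends on these tables. Protocol 10.6 limits summaries after premature termination to parameters needed for the development program or for regulatory reporting. Re-basing would not make an uncontrolled change attributable to PRALUENT: in the simulation, many patients are still flagged from the OLE baseline with no drug effect at all.

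Most of this stands, and it limits the remedy. It does not remove the labelling problem, because in a descriptive safety study the tables are the result. Early termination can only shorten follow-up, and at shorter follow-up the pre-OLE share of the interval is larger.

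Three stronger readings are tempting and are not supported:
- That no safety table is re-based. The ALT increase uses the OLE baseline and feeds the PCSA and liver-injury analyses (SAP 5.7.2); new-onset diabetes excludes parent-period diabetes.
- That 80% or 67% of the reported change is placebo artefact. Those figures describe time only.
- That the primary endpoint is compromised. AE incidence is counted from the first OLE dose and does not rest on this laboratory or vital-sign baseline.

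**Conclusion.** The concern holds in limited form and is worth fixing. The mechanism follows directly from SAP 5.7 and 6.1 and protocol 10.5, read with the TEAE period in SAP 4.7.1. It affects, for ex-placebo patients and for their part of Overall:
- change summaries for the general laboratory, vital-sign and weight parameters;
- the creatinine, hemoglobin, weight, heart-rate, SBP and DBP change criteria;
- the normal/missing-at-baseline row of the laboratory PCSA table.

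Only the offset of about 96 weeks and the time shares are fixed by the documents. The number of misattributed flags depends on lasting change during the placebo period, which the documents do not report, and it may be zero. Separately, SAP 4.7 and the two Day 1 statements in Appendix 10.1 conflict with SAP 5.7 and 6.1 whatever the size of the effect.

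**What to change.** In the SAP:
- Add change-from-baseline summaries, change-based PCSA summaries and the laboratory PCSA table by baseline status, using the last value before the first OLE dose (parent EOS / OLE day 1), at least for the ex-placebo group. Use these to describe OLE-emergent change.
- Keep the parent baseline for lipid percent change and for cumulative-exposure summaries in ex-PRALUENT patients. Keep the ALT exception.
- State the baseline in the title of every table.
- Align SAP 4.7, 5.7, 6.1, 6.3 and Appendix 10.1, and record the difference from protocol 10.5 in SAP 1.2.3. No protocol amendment is needed for this.

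**Cost.** One more baseline flag, SAP wording and a limited set of descriptive tables, kept within the reduced reporting scope of protocol 10.6. No new data are needed: vital signs and weight are scheduled on day 1 (protocol Table 1), and day-1 laboratory values come from the parent EOS visit (protocol 8.1.1, footnote 7). The added tables remove placebo-period carry-over. Their text should say that the remaining change is still uncontrolled.

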5.7.1. Analysis of Adverse Events

In general, the primary focus of AE reporting will be on TEAEs. Pre-treatment and post-treatment AEs will be provided separately.

If an AE date/time of onset (occurrence, worsening, or becoming serious) is incomplete, an imputation algorithm will be used to classify the AE as pre-treatment, treatment-emergent, or post-treatment. The algorithm for imputing date/time of onset will be conservative and will classify an AE as treatment-emergent unless there is definitive information to determine pre-treatment or post-treatment status. Details on classification of AEs with missing or partial onset dates are provided in Section 6.4.

Adverse event incidence tables will present the number (n) and percentage (%) of patients experiencing an AE by SOC, HLGT (when applicable), HLT (when applicable), and PT. Multiple occurrences of the same event in the same patient will be counted only once in the tables within a treatment phase. For tables presenting severity of events, the worst severity will be chosen for patients with multiple instances of the same event. The denominator for computation of percentages is the safety population within each patient group.

The table of all TEAEs presented by SOC and PT will be sorted by the internationally agreed SOC order and decreasing frequency of PTs within SOCs (in the PRALUENT group). This will define the presentation order for all other tables by SOC and PT, unless otherwise specified. The tables of AEs by SOC, HLGT, HLT and PT will be sorted by the SOC internationally agreed order and the other levels (HLGT, HLT, PT) will be presented in alphabetical order, unless otherwise specified.

Analysis of all treatment-emergent adverse events

The following TEAE summaries will be generated:

- Overview of TEAEs, summarizing number (%) of patients with any
 - TEAE;
 - Serious TEAE;
 - TEAE leading to death;
 - TEAE leading to permanent treatment discontinuation.
- All TEAEs by primary SOC, HLGT, HLT, and PT
- Number (%) of patients experiencing common TEAE(s) presented by primary SOC, HLT and PT (HLT incidence ≥ 5 % in the total patient group), sorted by SOC internationally agreed order and by alphabetic order for the other levels (HLT and PT);
- All TEAEs by primary SOC and PT, sorted by the internationally agreed SOC order and by decreasing incidence of PTs within each SOC (in the PRALUENT group).
- All TEAEs regardless of relationship in one column and, in the same table a second column with TEAEs related to alirocumab according to investigator's opinion by primary SOC, HLGT, HLT and PT;
- All TEAEs by maximal severity (i.e., mild, moderate or severe), presented by primary SOC and PT, sorted as defined above;
- The event rate per patient-year (the number of patients with an event in question divided by total patient-years) will be provided for all TEAEs by SOC and PT. For a patient with event, patient year is censored at time of first event; for patient without event, it corresponds to length of TEAE period;
- Kaplan-Meier curves will be provided, when appropriate, for time from first dose of study treatment to the first occurrence of selected TEAEs as well as incidence

rates at 48, 96, 144, and 192 weeks of exposure. Patients without any event will be censored at the end of the TEAE period. Selected TEAEs could be AESIs (e.g neurocognitive events), or TEAE related to any clinically significant signal that needs further characterization;

The frequency of selected AEs by SOC and PT over time during the treatment period (number of patients experiencing AE and percentage by patient-months) will be provided, when appropriate, by time intervals defined as: ≤48 weeks, >48 to ≤96 weeks, >96 to ≤144 weeks, >144 to ≤192 weeks, using the PROC LIFETEST with the actuarial method. Only the first event will be counted.

Analysis of all treatment emergent serious adverse event(s)

- All serious TEAEs by primary SOC, HLGT, HLT, and PT and by SOC/PT; Patient listings of serious TEAEs will be provided for the report appendix.
- All serious TEAEs regardless of relationship in one column and in the same table a second column with TEAEs related to alirocumab according to investigator's opinion, by primary SOC, HLGT, HLT, and PT;
- The event rate per patient-year will be provided for all serious TEAEs by SOC and PT.

Analysis of all treatment-emergent adverse event(s) leading to treatment discontinuation

• All TEAEs leading to permanent treatment discontinuation, by primary SOC, HLGT, HLT, and PT and by SOC/PT; Patient listings of TEAEs leading to permanent treatment discontinuation will be provided for the report appendix.

Analysis of groupings of adverse events including selected adverse events of special interest

- All grouping of TEAEs including adverse events of special interest, as listed in Section 4.7.1.2, will be presented by SMQ/CMQ and PT (when selection is based on SMQs/CMQs) and by SOC and PT (when selection is based on the e-CRF tick box or HLGT/HLT). The summaries will be sorted by decreasing incidence of PT within each SOC/SMQ (in the PRALUENT group).
- Neurocognitive events adjudicated by the neurocognitive events review committee will also be summarized by primary SOC and PT. They will also be summarized according to the adjudication of possible etiology of the neurocognitive events (Yes/No) (Section 4.7.1.2).
- All TEAEs within diabetes grouping will be analyzed overall and according to the diabetic status at baseline.
The following variables will also be tabulated for the local injection site reactions TEAEs:

- Intensity of the event (mild, moderate, severe);
- Number of events divided by the number of study treatment injections received;
- Time from first study treatment injection to first injection site reaction;
- Description of the highest intensity of each symptom recorded in the specific e-CRF page with table and bar chart.

Description of symptoms and possible etiologies for General Allergic Reaction TEAE reported by investigator (using the tick box), will be presented.

Post-treatment adverse events

- All post-treatment AEs by primary SOC and PT, sorted by the internationally agreed SOC order and decreasing incidence of PTs (in the PRALUENT group) within each SOC;
- All post-treatment SAEs by primary SOC and PT, sorted by the sorting order defined above.

Subgroup of patients with two consecutive LDL-C <25 mg/dL (<0.65 mmol/L)

If applicable, similar summaries of TEAEs as those described above will be provided on the safety subgroup population of patients with two consecutive results of LDL-C <25 mg/dL (as defined in Section 4.8) in both patient groups. Only TEAEs for which it will be confirmed or unclear that they occurred, worsened or became serious on the day or after the day the first level of LDL-C <25 mg/dL was observed will be considered in this summary.

In addition, the neurocognitive event rate in patients with 2 consecutive results separated by at least 21 days for calculated LDL-C <25 mg/dL, and calculated LDL-C <15 mg/dL, will be assessed.

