1.1. Background/Rationale

This study is an open-label extension (OLE) to the neurocognitive function study (R727-CL-1532) in which all patients will be treated, in a single arm, with PRALUENT. The study will be conducted on patients who completed treatment and the end of study (EOS) visit in the neurocognitive function study (R727-CL-1532), with no premature discontinuation of study drug or placebo. This will allow for patient exposure to PRALUENT of approximately 6 years.

At the time of inclusion into the OLE study, knowledge of the treatment arm in the neurocognitive function study (R727-CL-1532) will not be available to the investigator or the sponsor. Patients eligible to participate in the OLE study will initiate treatment with PRALUENT at the starting dose of 75 mg once every 2 weeks (Q2W), regardless of the treatment group to which they were randomized in the neurocognitive function study (R727-CL-1532).

The study duration of approximately 192 weeks, in addition to the 96-week exposure in the neurocognitive function study (R727-CL-1532), will enable the assessment of long-term exposure to PRALUENT.

Following a Type II variation for Praluent submitted on 14 August 2019 to modify the EU RMP, the missing information "clinical impact of very low LDL-C for extended period of time" was removed from the RMP in the CHMP opinion dated Jan. 16,2020. The EMA agreed to release the R727-CL-1609 study as there is no expectation that this study can further characterize the safety profile of alirocumab beyond what has already been learned from other long-term, controlled studies. Therefore, the study was terminated early by sponsor on January 31, 2020. Given this early termination, all analyses will be considered descriptive.

PRALUENT is also referred to as alirocumab, REGN727 or SAR236553. In the context of the R727-CL-1609 SAP, it will be referred to as PRALUENT.

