4.6.1. Primary Endpoint

The primary endpoint in the study is the incidence of AEs after first administration of study drug through the last dose of study drug plus 2 weeks.

The following AEs will be described:

- AEs/serious adverse events (SAEs)
- AEs leading to treatment discontinuation
- Adverse events of special interest (AESI)

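### The SAP commits to no exposure-adjusted estimate for AESI groupings other than injection site reactions, although the study stopped early

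*SAP*

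**What the plan says.** SAP 4.6.1 defines the outcome: "The primary endpoint in the study is the incidence of AEs after first administration of study drug through the last dose of study drug plus" a further fortnight. It names three things to be described: AEs and SAEs, "AEs leading to treatment discontinuation", and AESIs.

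SAP 1.1 records that "the study was terminated early by sponsor on January 31, 2020". The planned observation period was about 192 weeks (SAP 2.1).

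SAP 5.7.1 sets the general rule for AE tables: "The denominator for computation of percentages is the safety population within each patient group". It then defines a rate, which is patients with the event divided by patient-years, with time stopped at the first event, or at the end of the TEAE period for patients without one. That rate is planned for all TEAEs by SOC and PT, and "The event rate per patient-year will be provided for all serious TEAEs by SOC and PT".

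For the other two named parts the same section says:

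- AESIs: "All grouping of TEAEs including adverse events of special interest, as listed in Section 4.7.1.2, will be presented by SMQ/CMQ and PT", or by SOC and PT where the selection uses a tick box or an HLGT/HLT. No rate is mentioned for the grouping.
- Discontinuations: "All TEAEs leading to permanent treatment discontinuation, by primary SOC, HLGT, HLT, and PT and by SOC/PT", plus listings. No rate is mentioned.

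Kaplan-Meier curves with incidence at 48, 96, 144 and 192 weeks, and an actuarial analysis by 48-week interval, are offered for selected events where judged suitable. AESIs are given as possible candidates. Separately, SAP 5.5.1 states without condition that treatment discontinuation due to AEs will be shown by Kaplan-Meier.

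**The concern.** A crude percentage of the safety population gives a patient followed for a few months the same weight in the denominator as one followed for several years. That does little harm when nearly everyone completes the same planned period. Here the planned period was cut short. Each patient's day 1 was their own final visit in the parent study (protocol 5.1), so calendar start dates need not coincide. Patients who permanently stop treatment also leave the study at the early termination visit (protocol 8.1.1, footnote 1). Unequal follow-up is therefore a reasonable inference, though the documents do not quantify it.

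At stake is whether the AESI results of a long-term, uncontrolled safety study can be read as a risk over a known time. Without a concurrent control, the reader depends on the denominator to make sense of each figure.

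**Working it through.** There is no sample size, power or event rate on this point in the documents, so there is no planned figure to reproduce. The check has three steps.

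**Step 1. What is committed, by type of event.**

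| Event type | Committed | Discretionary |
|---|---|---|
| All TEAEs, serious TEAEs (SAP 5.7.1) | n (%), patient-year rate by SOC and PT | Kaplan-Meier, actuarial |
| TEAEs leading to discontinuation (5.7.1, 5.5.1) | n (%), listings, Kaplan-Meier graph | none stated specifically |
| Injection site reactions (5.7.1) | n (%), events per injection, time to first reaction | Kaplan-Meier, actuarial |
| Other AESI groupings (4.7.1.2, 5.7.1) | n (%) | Kaplan-Meier, actuarial |

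Protocol 10.4.4.1 ties the AESI Kaplan-Meier analysis to a detected signal that warrants further characterization. That is somewhat circular, because judging whether there is a signal already calls for a measure scaled to follow-up.

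**Step 2. Can the PT-level rates fill the last row?**

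- A patient with two PTs from the same SMQ or CMQ counts once in the grouping but once in each PT rate, so numerators cannot be summed.
- Person-time is stopped separately at the first event of each PT. The grouping needs time to the first event of any PT, which the PT table does not contain.
- The hypersensitivity, neurologic and neurocognitive groupings all take in many terms (SAP 4.7.1.2, Appendix 10.3).
- The ALT criterion comes from laboratory data, and new-onset diabetes can be met by HbA1c or fasting glucose alone (4.7.1.2). A TEAE table by PT cannot supply either. New-onset diabetes is also limited to patients without diabetes at baseline or during the parent study, so it needs its own person-time.

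**Step 3. How much the crude percentage can move (assumed values).**

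Assume a constant event rate l per year and follow-up uniform from a to b years. Neither is in the documents.

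- Cumulative incidence at T: 1 - exp(-l*T), with T = 192 x 7 / 365.25 = 3.68 years.
- Crude percentage: 1 - [exp(-l*a) - exp(-l*b)] / [l*(b - a)].

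At l = 0.01 (1 per 100 patient-years), the 192-week cumulative incidence is 1 - exp(-0.0368) = 3.61%. For follow-up uniform over 48-192 weeks, a = 0.920 and b = 3.680, so the crude percentage is 1 - (0.99084 - 0.96387)/0.02760 = 2.27%. The other cases follow in the same way:

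| Assumed rate per year | 192-week incidence | Crude, 48-192 wk | Crude, 48-144 wk | Crude, 24-96 wk |
|---|---|---|---|---|
| 0.005 | 1.82% | 1.14% | 0.92% | 0.57% |
| 0.01 | 3.61% | 2.27% | 1.82% | 1.14% |
| 0.02 | 7.10% | 4.48% | 3.61% | 2.27% |
| 0.05 | 16.81% | 10.79% | 8.76% | 5.57% |

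At 0.01 the ratios are 3.61/2.27 = 1.6, 3.61/1.82 = 2.0 and 3.61/1.14 = 3.2. The other rows give nearly the same ratios.

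Under a constant rate, expected patient-years to first event or end of follow-up equal the event probability divided by l. In the 48-192 week case that is 0.0227/0.01 = 2.27 years per patient, and 0.0227/2.27 returns 0.01. The SAP's own rate therefore recovers the same value under each follow-up pattern, which the percentage does not.

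**The case against.** The strongest case against is that the SAP already handles follow-up in several places, the study is descriptive, and the regulator released it because it was not expected to add to the known safety profile (SAP 1.1). Protocol 10.6 allows reduced reporting after early termination. Exposure is tabulated in 4-week bands (SAP 4.5 and 5.5.1), so readers can see the follow-up behind each percentage. Conditional Kaplan-Meier for AESIs matches the graded approach in protocol 10.4.4.1 and looks deliberate.

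Much of this limits the point, and four stronger readings should be set aside:

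- A reader might infer that AESIs and discontinuations get nothing but crude percentages. For discontinuations that is wrong, because SAP 5.5.1 commits to Kaplan-Meier. For AESIs it overstates. Injection site reactions have two further measures, pregnancy is a single PT and so is covered by the all-TEAE rate if reported as a TEAE, and a neurocognitive event rate is promised for patients with two consecutive low LDL-C results. That last rate covers only a subgroup, and its denominator is not defined.
- A reader might set half a year of follow-up (1 - exp(-0.005) = 0.50%) against the full 3.68 years (3.61%) and speak of a 7-fold distortion. Those are extreme fixed durations, not a description of this study.
- A reader might take 31 January 2020 as a common last day of follow-up. The SAP gives it as the date of termination only, and the COVID-19 disposition categories in SAP 4.4 suggest that visits may have continued after it.
- A reader might infer that the comparison of former placebo and former PRALUENT patients is biased. Nothing in the documents shows that follow-up differs between those groups.

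What the objection does not answer is the remaining AESI groupings. A descriptive analysis still needs an interpretable denominator. An exposure table for the whole population does not give person-time to first event for a grouping. Discretion exercised in an open-label study can also be exercised after the data have been seen.

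**Conclusion.** The point holds for AESI groupings other than injection site reactions. They are a named part of the primary endpoint, yet the SAP, which itself records the early stop, assures them only of n (%) of the safety population. The PT-level rates cannot be turned into grouping rates. For TEAEs leading to discontinuation the gap is minor: a Kaplan-Meier graph is promised, and only a patient-year rate is missing.

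Under the assumed follow-up patterns, the crude percentage falls below the 192-week cumulative incidence by a factor of about 1.6 to 3.2. This rests on a constant event rate and uniform follow-up. The actual follow-up distribution is not stated, so the true factor could lie outside that range. No result is invalidated. This is a cheap improvement that makes the AESI results readable as rates.

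**What to change.** In SAP 5.7.1, under the analysis of AE groupings, state that the patient-year rate already defined there (patients with a first event divided by patient-years, time stopped at first event) will be given for each AESI grouping in 4.7.1.2. Show it beside n (%), by parent-study treatment group and overall.

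Two details need a sentence each:

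- For new-onset diabetes, restrict numerator and person-time to patients without diabetes at baseline as 4.7.1.2 defines them.
- For the laboratory-defined events, name the date that counts as onset. Section 4.7.1.2 does not say which date applies when two qualifying values are required.

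Optionally, add the same rate for TEAEs leading to permanent discontinuation, to accompany the graph in 5.5.1.

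The cost is a few table columns using a calculation that the SAP already requires, with no new data and no design change. The downside is slightly longer tables.
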